8.3 Clinical Laboratory Evaluation

Clinical laboratory test results (blood chemistry/coagulation, hematology and urinalysis) will be listed for individual subjects. Baseline for clinical laboratory parameters will be defined as the last evaluation before dosing with study treatment. For each individual lab test value, the raw value and change from baseline will be summarized by treatment and time point.

Each clinical laboratory test will be defined by the clinical laboratory to be “Low”, “Normal”, or “High”, according to the normal reference range from the clinical laboratory. The number and percentage of subjects who have a shift from within to outside the normal reference range from baseline (and vice versa) to each follow-up visit will be summarized by treatment and time point.

8.4 Vital Signs

Vital signs results including BP (systolic and diastolic), pulse rate, respiration rate, and body temperature will be listed for individual subjects. Baseline for vital signs measurements will be defined as the last evaluation before dosing with study medication. Summary statistics, including change from baseline, will be determined for each measure and will be summarized by treatment and time point.

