Evaluated Parameters/Outcome Measures:

Primary:	
Safety:
 
 1. Adverse events, physical examination (PE), vital signs, electrocardiogram, Surgical Site assessments, neurosensory testing (neurosensory assessments at site of incision and the skin surrounding the incision and neurosensory monitoring will be performed at 24 and 48 hours post-infiltration, and at follow up clinic visits), clinical labs (standard hematology, clinical chemistry/coagulation, urinalysis), concomitant medications. 
Pharmacokinetics:
 
 2. Plasma samples to measure appropriate analyte concentrations will be collected from all subjects. The PK time points will be adequate to determine the PK profiles of the following analytes: 
 • CA-008 • CA-101 • Capsaicin • Capsaicin-glucuronide 
The time points for collection are at baseline (before dosing), and at 5 minutes, 15 minutes, 30 minutes, 45 minutes, and 1, 1.5, 2, 2.5, 3, 3.5, 4, 6, 8, 12, 16, 24, 36, and 48 hours after dosing.

-----------------	--

Secondary:	
 1. Pain as assessed by a standard 11-point (0–10) NPRS at post-infiltration time points of 15, 30, 45 min, 1, 2, 4, 8, 12 hours, then every 4 hours (if awake at time of assessment) until discharge or ET. Subjects will report pain twice daily through Day 15 or early termination (method of reporting – Subject Diary). 2. Use of postoperative analgesic therapy/treatments and NPRS scores prior to use of the analgesics will be collected during the study period through Day 15 or early termination (by site staff during in-patient stay, and via Subject Diary during outpatient portion).
Endpoints: Primary (Safety):	
 1. Incidence and severity of abnormalities in physical / neurosensory examination, vital signs, ECG, Surgical Site assessments, or clinical labs. 2. Incidence and severity of adverse events and serious adverse events.

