The clinical laboratory tests will be completed at Screening, Prior to surgery, and at 1.5 hours (± 0.5 hour) after the administration of study medication. In addition to the clinical laboratory tests, a serum pregnancy test will be performed at the Screening Visit and a urine pregnancy test will be performed prior to surgery for women of childbearing potential. ALT or AST $> 3 \times$ ULN / Tot. Bili $> 2 \times$ ULN/ Alk Phos. $> 2 \times$ ULN will be considered an adverse event, as well as any other changes deemed clinically significant by the Investigator.

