3 GENERAL ANALYSIS AND REPORTING CONVENTIONS

This section discusses general policies to be employed in the analysis and reporting of the data from the study. Departures from these general policies may be provided in the specific detailed sections of this SAP. When this situation occurs, the rules set forth in the specific section take precedence over the general policies.

Each active dose cohort will be presented separately, along with a combined active dose group. Placebo subjects will be pooled across all cohorts in all summaries and analyses.

All continuous study assessments will be summarized by treatment and time point (as applicable) using the descriptive statistics n, mean, SD, median, and range (minimum, and maximum). All of the categorical study assessments will be summarized by treatment and time point (as applicable) using frequency counts and rates of occurrence (%). Changes from baseline for continuous outcomes will be presented as their corresponding continuous measures for post-baseline visits. All study data will be listed by dose cohort, subject, and time point (as applicable).

No preliminary rounding will be performed; rounding will only occur after the analysis. To round, consider the digit to the right of the last significant digit: if <5 , then round down; if ≥ 5 , then round up. Means and medians will be presented with one more decimal place than the precision of the data. Standard deviations will be presented with two more decimal places than the precision of the data. Percentages will be presented with one decimal place. A percentage of 100% will be

reported as 100%. Minimums and maximums will be presented with the same precision as the original data.

All analyses will be performed using the SAS System® version 9.3 or higher. The domain (Study data tabulation Model [SDTM]) and analysis (Analysis Data Model [ADaM]) data sets will be taken as input to the SAS programs that generate the report-ready tables, figures and listings. The submission ready SDTM and ADaM data sets will be provided to the sponsor along with display deliveries. The specifications for the domain data sets and analysis data sets will be provided in a separate document.

The following conventions will be used throughout the study analysis:

- Time T0 is the time of completion of study drug administration.
- Assessment visit times are defined by time T0.
- Baseline value is defined as the last valid measurement prior to beginning study drug administration.

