| Table 14.2.8.2.2 | Safety Population | Summary of Percent of Subjects Using Rescue Medication by Day up to Discontinuation of Efficacy Portion |
| Table 14.2.9 | Safety Population | Kaplan-Meier Analysis of Time to First Use of Rescue Medication by Dose (if needed) |
| Table 14.3.1.1 | Safety Population | Overall Summary of Treatment-Emergent Adverse Events (TEAEs) |
| Table 14.3.1.2 | Safety Population | Summary of TEAEs by System Organ Class and Preferred Term |
| Table 14.3.1.3 | Safety Population | Summary of Treatment Related TEAEs by System Organ Class and Preferred Term |
| Table 14.3.1.4 | Safety Population | Summary of SAEs by System Organ Class and Preferred Term |
| Table 14.3.1.5 | Safety Population | Summary of TEAEs Leading to Discontinuation from Study |
| Table 14.3.1.6 | Safety Population | Summary of TEAEs by System Organ Class, Preferred Term and Severity |
| Table 14.3.1.7 | Safety Population | Summary of TEAEs by System Organ Class, Preferred Term and Relationship to Study Drug |
| Table 14.3.2.1.1 | Safety Population | Summary of Blood Chemistry/Coagulation Laboratory Tests: Results and Change from Baseline |
| Table 14.3.2.1.2 | Safety Population | Summary of Blood Chemistry/Coagulation Laboratory Tests: Shifts from Baseline |
| Table 14.3.2.2.1 | Safety Population | Summary of Hematology Laboratory Tests: Results and Change from Baseline |
| Table 14.3.2.2.2 | Safety Population | Summary of Hematology Laboratory Tests: Shifts from Baseline |
| Table 14.3.2.3.1 | Safety Population | Summary of Urinalysis Laboratory Tests: Results and Change from Baseline |

| | | |
|------------------|-------------------|--|
| Table 14.3.2.3.2 | Safety Population | Summary of Urinalysis Laboratory Tests: Shifts from Baseline |
| Table 14.3.4 | Safety Population | Summary of Vital Signs: Results and Change from Baseline |
| Table 14.3.5 | Safety Population | Summary of Surgical Site Assessment |
| Table 14.3.6.1 | Safety Population | Summary of Neurosensory Exam –Target Foot |
| Table 14.3.6.2 | Safety Population | Summary of Neurosensory Exam –Non-Target Foot |
| Table 14.3.7 | Safety Population | Summary of ECG Exam Abnormal Findings |

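### The SAP neither counts nor grades subjects with abnormal vital signs and gives no severity for laboratory abnormalities, although the first primary safety endpoint is the incidence and severity of such abnormalities

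*SAP*

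**What the plan says.** The protocol synopsis lists two primary safety endpoints. The first is "Incidence and severity of abnormalities in physical / neurosensory examination, vital signs, ECG, Surgical Site assessments, or clinical labs". The second, a separate item, is "Incidence and severity of adverse events and serious adverse events".

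For vital signs, SAP 8.4 plans individual listings and then: "Summary statistics, including change from baseline, will be determined for each measure and will be summarized by treatment and time point". SAP section 3 defines the default summary of a continuous measure, "using the descriptive statistics n, mean, SD, median, and range (minimum, and maximum"). The SAP 14.1.1 list has one vital-sign table, 14.3.4: "Summary of Vital Signs: Results and Change from Baseline".

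For laboratory tests, SAP 8.3 adds a shift analysis: "The number and percentage of subjects who have a shift from within to outside the normal reference range from baseline", and the reverse, by treatment and time point.

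The protocol already has tools for counting and grading. Section 10.5.4 sets cut-offs for high and low systolic pressure, high diastolic pressure and high heart rate. Appendices G and H give Grade 1 to 4 scales for vital signs and laboratory values, and the stopping rules in protocol 8.4 refer to both. No analysis section of the SAP uses either scale.

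**The concern.** An endpoint defined as incidence and severity needs a number of subjects and a grade. For vital signs the SAP gives neither, and for laboratory values it gives a number without a grade. Followed exactly, the plan leaves those parts of a primary endpoint unreported.

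Safety and tolerability is a primary objective, and each dose has only six active subjects. What a reader of the report will want is how many subjects at each dose had, for example, a Grade 3 systolic pressure, and whether that number rises with dose. No planned table shows it.

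**Working it through.** **Step 1. Set each component of endpoint 1 beside the SAP.**

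| Component | SAP text and table | Incidence | Severity |
|---|---|---|---|
| Vital signs | 8.4; 14.3.4 | No | No |
| Laboratory tests | 8.3; results and shift tables 14.3.2.1.1 to 14.3.2.3.2 | Yes, as shifts out of range | No |
| ECG | 8.8; 14.3.7 | Yes, subjects with abnormal results | Not graded |
| Neurosensory | 8.7; 14.3.6.1 and 14.3.6.2 | Yes, normal/abnormal counts | Not graded |
| Surgical site | 8.6; 14.3.5 | Abnormalities summarised | Scores summarised |
| Physical examination | 8.5 | Listed only | Listed only |

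Vital signs are the one component with numerical cut-offs and a grading scale in the protocol but no count in the SAP.

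**Step 2. Can Table 14.3.4 be read back into an incidence?** Protocol 10.5.4 schedules inpatient readings at 0.5, 1, 1.5, 2, 4, 6, 8, 10, 12, 16, 20, 24, 28, 32, 36, 40, 44 and 48 hours, which is 18 time points, with three more at Days 8, 15 and 29.

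The following figures are assumed for illustration. Six active subjects all have a baseline systolic pressure of 120 mmHg. At each of six time points exactly one subject reads 165 mmHg (Appendix G Grade 3, above 155) and the other five stay at 120. At each affected time point:

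- mean change = (165 − 120)/6 = 45/6 = +7.5 mmHg
- SD of change = √[(37.5² + 5 × 7.5²)/5] = √337.5 = 18.4 mmHg
- median change = 0, minimum 0, maximum +45; highest value 165

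In the combined active group of 5 × 6 = 30, with no change in anyone else, the mean change is 45/30 = +1.5 mmHg.

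Now take two patterns. In A, the same subject has all six spikes. In B, each of the six subjects has one. Every statistic above is identical at every time point. The incidence of Grade 3 is 1/6 = 16.7% in A and 6/6 = 100% in B. The table shows that an extreme occurred and when, but it cannot give the number of subjects.

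**Step 3. Do the AE tables supply the count?** Under protocol 10.5.4 a value beyond a cut-off is an AE only if the investigator also considers it clinically significant. The cut-offs also cover less than Appendix G. Systolic above 150 and diastolic above 95 start at Grade 2, so Grade 1 (141–150 and 91–95) lies below them. Bradycardia, fever and respiratory rate are graded in Appendix G but have no cut-off in 10.5.4.

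**Step 4. Laboratory tests.** Protocol 10.5.1 says: "The clinical laboratory tests will be completed at Screening, Prior to surgery, and at 1.5 hours" after dosing. With one scheduled post-dose draw, a shift table at that time is close to the incidence of new out-of-range values. It misses worsening in subjects already out of range at baseline, and it does not separate a trivial crossing from a Grade 3 value.

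**The case against.** The best defence is that the SAP follows the protocol's own analysis sections. Protocol 10.6.1 names vital-sign measurements and laboratory results as safety endpoints, without mentioning incidence or severity, and 13.4.8 plans descriptive summaries for vital signs. This stands to the extent that the mismatch begins inside the protocol. It does not remove the synopsis endpoint. Section 13.4.8 leaves the detail to the SAP, and SAP section 12 records no change to what was planned.

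Second, much is already visible. Maxima by time point would show the 165 mmHg and the +45 in the example, and every value is listed by subject, which can be read with six active subjects per dose. That is true, and a reader who infers from the mean alone that such a spike would disappear from every vital-sign table would be wrong. What is missing is the count of subjects by dose; a listing leaves the reader to make it.

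Third, some laboratory severity does arrive through AEs. Protocol 10.5.1 makes its limits for transaminases, bilirubin and alkaline phosphatase AEs with no stated condition of investigator judgement, and SAP 8.2 tabulates TEAEs by maximum severity. This narrows the laboratory gap for those tests only.

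Fourth, Appendices G and H come from guidance for vaccine trials in healthy volunteers, and the protocol invokes them for stopping, not for summary tables. Appendix G calls a respiratory rate of 17–20 Grade 1. Appendix H as shown has no haematology, coagulation or urinalysis grades and none for LDH, GGT, uric acid or chloride, all of which are collected. These limits are real and shape the fix, but these are the only numerical severity scales for vital signs and laboratory values in the documents.

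**Conclusion.** The point holds in a limited form. For vital signs, neither the incidence nor the severity of abnormalities is planned. For laboratory tests, incidence is planned and severity is not. Two components of a primary safety endpoint are affected. The 1/6 against 6/6 comparison shows how far the planned table can leave the incidence undetermined; it rests on assumed pressures and does not predict that CA-008 raises blood pressure, which the documents do not claim.

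Two stronger inferences are not supported. A reader might conclude that endpoint 1 is not produced at all, but laboratory shifts and the ECG, neurosensory and surgical-site abnormalities are summarised. A reader might also conclude that dose-escalation decisions lacked graded data. The SAP governs the final study report, and both documents leave the details of the DMC's review to its charter, so nothing can be said about that here.

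The change should be made before database lock. It affects the completeness of safety reporting and does not call the conduct of the trial into question.

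**What to change.** 1. In SAP 8.4 and 14.1.1, add a table by treatment (each dose, combined active, pooled placebo) of the number and percentage of subjects by worst post-dose Appendix G grade against baseline grade, for each vital sign. Add rows for subjects crossing each protocol 10.5.4 cut-off at any post-dose reading, whether or not an AE was recorded.
2. In SAP 8.3 and 14.1.1, add a similar worst-grade table for the collected tests that Appendix H covers: sodium, potassium, calcium, glucose, BUN, creatinine, albumin, ALT, AST, alkaline phosphatase and bilirubin. Keep the shift tables for the rest.
3. State how grades that cannot be read from a measurement are assigned. Most Grade 4 entries in Appendix G are events such as an emergency visit or hospitalisation, so they must come from AE records.

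The cost is SAP wording and two programmed tables from data already collected, with no change to conduct. The small downside is that some ordinary values will appear as Grade 1; showing the baseline grade deals with this.

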8.5 Physical Examination

Physical examination abnormality results will be listed for individual subjects.

8.6 Surgical Site Assessment

The surgical site abnormality results and assessment score results will be listed and will be summarized by treatment and visit.

8.7 Neurosensory Assessment

The neurosensory assessment results will be listed and the number of subjects with normal/abnormal assessments will be summarized descriptively by treatment and time point.

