5.1.2. Background Information on the Use of Capsaicin in Analgesia

While capsaicin is well understood to have long lasting analgesic benefits, it has shown a limited effect in the initial hours following administration in both nonclinical (Dudley-Cash et al., 2012) and clinical studies (Savage et al., 2009; Pollak et al., 2009). In Phase 3 clinical trials conducted by Anesiva, capsaicin instillation demonstrated statistically significant reductions in cumulative pain and opioid use over 48 hours, but failed to show a difference with shorter periods of observation (e.g. pain AUC 4-32 hours). Activation of TRPV1 receptor with an agonist such as capsaicin immediately results in hyperalgesia, erythema, and localized burning sensation. Subsequently, exposure of the receptor to capsaicin leads to a functional desensitization that results in less response to both spontaneous and evoked painful stimuli. This desensitization leads to a sustained analgesia for a long period of time. Given its rapid conversion to capsaicin, a similar profile would be expected following the administration of CA-008 alone.

It is anticipated that CA-008 will be used with a standard of care multimodal analgesia (systemic medications +/- local anesthetic administered by regional block or local infiltration) to manage pain for the first 24 hours after which the TRPV1 agonism may provide adequate pain relief. Alternatively, CA-008 may be used with co-administration of other standard of care local anesthetics to improve analgesia in the initial hours after surgery. Concentric is initially planning to confirm the efficacy of CA-008 as a monotherapy in combination with standard of care systemic analgesic therapy or peripheral nerve blocks for treatment of post-surgical pain for periods of up to 96 hours.

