10.5.8. Neurosensory Exam

A Neurosensory Exam of the Foot and Great toe (bilateral) will be conducted at screening, baseline and then at 24 hours (± 2 hours) and 48 hours (± 4 hours) after the administration of study medication. The exam will involve the dorsal aspect of the great toe, midway between the nail fold and the DIP joint.

This evaluation will include the following (details described in [Appendix K](#)):

- Visual exam of the foot
- Deep Tendon Reflexes (normal, reduced or absent)
- Vibratory sensation (normal, reduced or absent)
- Monofilament Sensation (normal, reduced or absent)
- Allodynia to brush (pain (allodynia), hyperesthesia, normal, reduced or absent)
- Hyperalgesia to pin (increased pain (hyperalgesia), hyperesthesia, normal, reduced or absent)

The Neurosensory Exam will also be performed at each of the Follow-up visits on Days 8, 15 and 29, or at the time of discontinuation, and on Day 36, if the visit is needed. [Appendix A](#)

A persistent sensory change after 3 days, such as allodynia or hyperalgesia will be reported as an AE. Numbness at or near the incision need not be considered an AE since this could occur as a result of tissue trauma and inflammation from the surgery.

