APPENDIX K: PHYSICAL / NEUROLOGICAL EXAMINATION OF THE FOOT AND GREAT TOE

For all assessments, the foot should be warm.

- **Foot Inspection:** The feet are inspected for evidence of excessively dry skin, callous formation, fissures, frank ulceration or deformities. Deformities include flat feet, hammer toes, overlapping toes, hallux valgus, joint subluxation, prominent metatarsal heads, medial convexity (Charcot foot) and amputation.
- **Vibration Sensation:** Vibration sensation should be performed with the great toe unsupported. Vibration sensation will be tested bilaterally using a 128 Hz tuning fork placed over the dorsum of the great toe on the boney prominence of the DIP joint. Patients, whose eyes are closed, will be asked to indicate when they can no longer sense the vibration from the vibrating tuning fork. In general, the examiner should be able to feel vibration from the hand-held tuning fork for 5 seconds longer on his distal forefinger than a normal subject can at the great toe (e.g. examiner's DIP joint of the first finger versus patient's toe). If the examiner feels vibration for 10 or more seconds on his or her finger, then vibration is considered decreased. A trial should be given when the tuning fork is not vibrating to be certain that the patient is responding to vibration and not pressure or some other clue. Vibration is scored as 1) present if the examiner senses the vibration on his or her finger for < 10 seconds, 2) reduced if sensed for ≥ 10 or 3) absent (no vibration detection.)
- **Deep Tendon Reflexes:** The ankle reflexes will be examined using an appropriate reflex hammer (e.g. Trommer or Queen square). The ankle reflexes should be elicited in the sitting position with the foot dependent and the patient relaxed. For the reflex, the foot should be passively positioned and the foot dorsiflexed slightly to obtain optimal stretch of the muscle. The Achilles tendon should be percussed directly. If the reflex is obtained, it is graded as present. If the reflex is absent, the patient is asked to perform the Jendrassic maneuver (i.e., hooking the fingers together and pulling). Reflexes elicited with the Jendrassic maneuver alone are designated "present with reinforcement." If the reflex is absent, even in the face of the Jendrassic maneuver, the reflex is considered absent.

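### The by-treatment neurosensory summary (SAP 8.7) is normal/abnormal only, so it cannot show direction of change for brush and pin, or grade for any graded test

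*SAP*

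**What the plan says.** Protocol 10.5.8 and the form in Appendix A define six items: visual exam, deep tendon reflexes, vibration, monofilament, brush and pin. Brush is recorded as "Allodynia to brush (pain (allodynia), hyperesthesia, normal, reduced or absent" and pin as "Hyperalgesia to pin (increased pain (hyperalgesia), hyperesthesia, normal, reduced or absent". Monofilament is "Monofilament Sensation (normal, reduced or absent", and reflexes and vibration use the same three levels. The visual exam is normal or abnormal.

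The exam is done at screening, before surgery, at 24 and 48 hours, on Days 8, 15 and 29, and on Day 36 only if that visit is needed. The first primary safety endpoint in the protocol synopsis covers both how often neurosensory abnormalities occur and how severe they are.

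SAP 8.7 has two parts: "The neurosensory assessment results will be listed", and "the number of subjects with normal/abnormal assessments will be summarized descriptively by treatment and time point". Tables 14.3.6.1 and 14.3.6.2 are split by target and non-target foot; their titles mention neither test nor category. SAP 3 has a general rule of frequency counts for categorical data, but it also gives precedence to the specific section. Its change-from-baseline rule covers continuous outcomes. SAP 8.3 plans shifts for laboratory tests; SAP 8.7 plans none.

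**The concern.** Protocol 5.1.2 attributes two opposite effects to the active moiety. On the one hand, "Activation of TRPV1 receptor with an agonist such as capsaicin immediately results in hyperalgesia, erythema, and localized burning sensation". On the other, later exposure leads to a "functional desensitization that results in less response to both spontaneous and evoked painful stimuli". The brush and pin scales can tell these apart. The planned group summary cannot.

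The loss direction also has a surgical background: protocol 10.5.8 accepts numbness near the incision as a possible result of the operation, which placebo subjects undergo too. Persistent allodynia or hyperalgesia, by contrast, is named there as reportable. A reader comparing doses needs the two directions apart.

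Grade is at stake as well. Reduced and absent become the same entry, as do hyperesthesia and allodynia, so the exam table can serve the incidence half of the endpoint but not the severity half.

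**Working it through.** There is no plan figure to reproduce, so the check sets what is recorded beside what is summarised and then shows the effect at the planned group sizes.

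**Categories recorded and kept.** Brush and pin have 5 levels each; reflexes, vibration and monofilament have 3 each.
- Recorded: 2 × 5 + 3 × 3 = 19 categories over five graded tests.
- If *abnormal* is per test: 5 × 2 = 10 cells. Direction is merged for brush and pin only. For the other three tests, abnormal can only mean loss. Grade is dropped for all five.
- If *abnormal* is per exam: 2 cells. Direction is also merged across tests, and an abnormal visual exam makes the whole exam abnormal. Appendix K says of foot inspection that "Deformities include flat feet, hammer toes, overlapping toes, hallux valgus, joint subluxation", and hallux valgus is the condition being operated on, so the target foot could count as abnormal before dosing.

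SAP 8.7 does not choose between these readings. The merging within brush and pin and the loss of grade occur under both.

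**Group sizes.** 6 active subjects per dose; pooled placebo 5 × 2 = 10 if all five cohorts are filled.

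**Formula.** Within one test a subject has one category, so abnormal % = increased % + decreased %. The active minus placebo difference in abnormal is therefore the difference in increased plus the difference in decreased. Opposite signs cancel; equal signs add.

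**Illustrations.** The documents give no rates, so all of these are assumed.
- Pin, two doses: 2/6 with increased pain at one and 2/6 absent at the other. Both print as 2/6 = 33% abnormal.
- Grade: 3/6 reduced at one dose and 3/6 absent at another. Both print as 3/6 = 50% abnormal.
- One dose against placebo: 3/6 increased and 0/6 decreased, against 0/10 increased and 5/10 reduced. The planned table shows 50% v 50%, a difference of 0. By direction it is 50% v 0% increased and 0% v 50% decreased.

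Range, in percentage points, with no increased response on placebo:

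| Active increased / decreased | Placebo decreased | Difference in abnormal | Difference in increased |
|---|---|---|---|
| 30 / 0 | 10, 30, 50 | +20, 0, −20 | +30 each time |
| 20 / 30 | 10, 30, 50 | +40, +20, 0 | +20 each time |
| 30 / same as placebo | 10, 30, 50 | +30, +30, +30 | +30 each time |

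The last row is the benign case: with equal loss in both arms nothing cancels. Even then the table does not show which direction produced the difference.

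**The case against.** The strongest reply is that little is lost. SAP 3 lists all study data by dose cohort, subject and time point, and with 6 active subjects per dose such a listing can be read by eye. This stands: a reader might infer that direction disappears from the report, and it does not. But a listing is not a by-dose summary, and the SAP chose to tabulate this exam.

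Second, the adverse event route carries part of the signal. The synopsis makes sensory deficits or clinically significant persistent change at discharge a neurologic adverse event, and protocol 10.5.8 does the same for change persisting beyond 3 days. These events are tabulated by preferred term and severity. This also stands in part. It does not cover a finding at 24 hours that has gone by discharge, and both places exempt numbness near the incision. The severity recorded there is that of the event, not the exam grade.

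Third, the pharmacology is tempting to over-read. A reader might infer that the table hides the immediate hyperalgesic phase. The first post-dose exam is at 24 hours, so that phase largely precedes it. What remains is later or persistent increased response.

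Fourth, full cancellation needs more loss on placebo than on active. Both arms have the same operation and the drug is expected to desensitise, so the documents give no reason to predict it. The examples show what the table cannot distinguish, not what is likely.

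Fifth, a reader might infer from Appendix K that every operated foot is abnormal at baseline and that this swamps the result. That matters only under the per-exam reading, and baseline counts could be printed beside later ones. They would not be a within-subject shift.

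**Conclusion.** The point holds in a limited form. As specified, the by-treatment summary of the exam cannot show direction for brush and pin, or grade for any of the five graded tests, and leaves open what unit *abnormal* refers to. Neither the listings nor the adverse event tables supply a by-dose summary of the 24 and 48 hour findings by direction or grade. That is a real gap for a primary safety endpoint that includes severity.

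Its size is modest. Two of six items merge opposite directions; the wider merging across tests depends on the per-exam reading. No data are lost, and no test is affected because safety is descriptive only. The table shells are not in the documents; if they already carry rows by category, the remaining task is to bring SAP 8.7 into line with them.

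**What to change.** In SAP 8.7 and the shells for Tables 14.3.6.1 and 14.3.6.2:

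- State that results are summarised per test.
- Tabulate each test by its recorded categories, by foot, dose and pooled placebo. Reflexes, vibration and monofilament: normal / reduced / absent. Brush and pin: preferably all five levels, and at least increased / normal / decreased. The three-way grouping restores direction but leaves their grade to the listings.
- Show the pre-surgery baseline and the shift from it at 24 h, 48 h and Days 8, 15 and 29.
- List Day 36 without a by-dose shift, since only subjects with insufficient wound healing at Day 29 return for it.
- Give the visual exam its own row, so that pre-existing hallux valgus does not drive the sensory count.

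The cost is SAP text and programming. No new data, change of sample size or added test is needed. The downside is longer tables with many sparse cells at 6 per dose.
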